In an attempt to answer the question as to whether patients with SLE have an increased risk of malignancy in comparison to the general population, several large studies have recently been conducted. In the Swedish cohort of patients with SLE, [Bjornadal et al](#) used hospital discharge data to demonstrate an increased relative risk of any malignancy in SLE patients that was 25% higher among SLE patients compared to the general population. Of note, this finding was driven primarily by the higher incidence of non-Hodgkins lymphoma (NHL) in the SLE population which had a relative risk that was 2.86-fold higher (95% CI 1.96, 4.04) than that of the general population. These findings have been subsequently confirmed by the Systemic Lupus International Collaborating Clinics research group (SLICC) in a larger international multi-center cohort study. Using Standardized Incidence Ratio (SIR) estimates, a small increase in all malignancies combined was observed (SIR, 1.15, 95% CI 1.05, 1.27) for SLE compared to that expected for the general population based on data from regional cancer registry linkages

(Bernatsky et al, 2005). Similarly, the increased risk for NHL was also demonstrated (SIR, 3.64, 95% CI 2.63, 4.93) in the SLE population compared to the general population. Unfortunately, no investigations have been able to establish the reason for the close association between SLE and malignancy. Potential considerations in this regard include abnormal immune activity early in the course of the disease, as well as cumulative exposure to immunosuppressive medications. In the SLICC international multi-center cohort study, the adjusted Hazard Ratio (HR) for overall risk of malignancy after administration of any immunosuppressive drug was 0.82 (95% CI 0.50-1.36). However, when specifically considering hematological malignancies (Bernatsky et al, 2009), there was a suggestion of an increased risk after immunosuppressive drug exposures particularly when the medication exposures were lagged by a period of 5 years (adjusted HR 2.29, 95% CI 1.02-5.15).

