6.1 Study Enrollment Evaluations

The following data will be collected at enrollment (baseline). Data collection for enrollment may be carried out over more than one clinical evaluation visit.

1. Written informed consent (including consent for the use and disclosure of research-related health information).
2. Demographics (eg, age, gender, race/ethnicity (where allowed by local regulation), smoking history, alcohol use)
3. Medical history (including SLE history). Note: To collect additional important information on potential suicidality-related events, should any of the psychiatric events marked with an asterisk in [Appendix 2](#) be present at enrollment, the investigator should complete the Possible Suicidality-Related History Questionnaire (PSRHQ) eCRF (see [Appendix 3](#)).
4. Potential Confounders for Malignancies and/or Infections List (refer to [Appendix 7](#)).
5. Obtain historical and current SLE medications (immunosuppressants, antimalarials, corticosteroids and biologics). The name of the each SLE medication and start and stop dates will be recorded. In addition, for corticosteroids, the prescribed dose will be recorded. If the patient is receiving BENLYSTA, the date of first dose, and route of administration (IV or SC) will be recorded as well as name of the other SLE medications the patient was receiving at the time BENLYSTA therapy was initiated.
6. SLEDAI 2000 (see [Appendix 6](#)). To complete SLEDAI 2000, data from the following laboratory tests if available: Hematology (WBC, platelets), complement (C3, C4), anti-dsDNA, routine urinalysis, and spot urine for macroscopic/microscopic/proteinuria assessments. Note: Laboratory values should not be attributed on the SLEDAI 2000 unless laboratory values were obtained within 30 days of enrollment otherwise the laboratory values will be noted as not done.
7. SLICC/ACR Damage Index ([Appendix 5](#)).
8. Hospitalizations occurring in the previous 6 months.

9. Confirm patient meets study eligibility criteria.

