8.3.2 Analysis of Primary Endpoints

In addition to analyses that consider initial treatment group (BENLYSTA cohort vs. comparison cohort), analyses that specifically account for changes in therapy (in either group) by considering a variety of risk windows will be employed. These analyses will attribute events to BENLYSTA treatment if they occur within the designated risk windows for BENLYSTA exposure and to comparison treatment otherwise. These analyses will allow for a registry patient to contribute person-time to both BENLYSTA treatment, and comparison treatment and as a result, will specifically account for treatment switching to BENLYSTA or from BENLYSTA. Switching between BENLYSTA and comparison treatment will be taken into account in a number of ways in the analysis and will be further defined within the statistical analysis plan. No new analyses for changing between BENLYSTA formulation or stratifying by BENLYSTA formulation are planned. Planned analyses are outlined below; all analyses will be detailed in the statistical analysis plan.

- Analysis by initial treatment group of rate per person years of observation time.
- Analysis by initial treatment group of rate per person years of exposure where BENLYSTA exposure ends 14 weeks (approximately 5 half-lives) after cessation of treatment.
- For serious psychiatric events, BENLYSTA exposure is all time on treatment with BENLYSTA ending 14 weeks (approximately 5 half-lives) after cessation of treatment, with all remaining treatment time attributed to the comparison cohort.
- For serious infections, opportunistic infections and other infections of interest, BENLYSTA exposure is all time on treatment with BENLYSTA ending 6 months after cessation of treatment, with all remaining treatment time attributed to the comparison cohort.
- For NMSC and malignancies excluding NMSC, analysis will be performed where all events will be attributed to BENLYSTA if the patient was ever exposed to BENLYSTA treatment prior to the event and attributed to the comparison cohort otherwise (ie, once exposed, always at risk).
- Mortality will be analyzed applying all the above-mentioned risk windows (eg, 14 weeks, 6 months, and ever-exposed).
- Other risk windows (including risk windows for comparison treatment) may also be assessed and defined in the statistical analysis plan.

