## 5. CONSIDERATIONS FOR DATA ANALYSES AND DATA HANDLING CONVENTIONS

### 5.1. Study Exposure & Sub-group Display Descriptors

Exposure Group Descriptions			
Study Exposure Group		Data Displays for Reporting	
Code	Description	Description	Order in TLF
A	BENLYSTA	BENLYSTA	2
B	NON-BENLYSTA	NON-BENLYSTA	1

Exposure group comparisons will be displayed using the following specified descriptors:

- BENLYSTA vs NON-BENLYSTA

BENLYSTA group is used for subjects who are exposed to Benlysta while NON-BENLYSTA group is used for subjects who are not exposed to Benlysta. For summary description of baseline characteristics, the exposure group represents subjects' exposure at enrollment (i.e 'Initial Exposure'). For summary of safety and effectiveness endpoints, the exposure group will be defined using the 'Initial Exposure', 'As-Exposed', and/or 'Ever-Exposed' strategies (see Appendix 2, Section 9.2). 'As-Exposed' is defined based on whether or not a subject is using Benlysta at specific period during the study follow-up time; thus a subject's exposure group can change over time depending on switching to or off Benlysta. 'Ever-Exposed' is defined based on whether a subject was exposed to Benlysta at any point in time after enrollment, in this instance a subject's exposure can change only once over time if they were initially 'Unexposed' and then started using Benlysta; once a subject is exposed to Benlysta, they will always be considered as 'Exposed'.

The specific strategy for defining exposure group and the analysis approach for accrued data will be indicated on the TLFs titles and list of the planned data displays provided in Appendix 11 (Section 9.11).

---

 Subjects are considered to have switched from BENLYSTA exposure group if they permanently discontinued Benlysta treatment or missed doses of Benlysta for more than 98 days and do not restart doses of Benlysta on or before day 99 after the last Benlysta medication end date. Subjects are considered to have switched from NON-BENLYSTA exposure group if they initiate or start receiving Benlysta dose anytime during the study follow-up period. Change of different study-qualifying Non-Benlysta Standard of Care (SOC) medications does not count as exposure switching.

Primary analysis will be done on ‘Initial Exposure’ strategy for all endpoints while ‘As--Exposed’ and ‘Ever-Exposed’ will apply for some endpoints as exploratory analysis:

Endpoints	Primary analysis		Exploratory analysis	

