### 9.2.1.3. Ever-Exposed

This exposure strategy accounts for whether a subject was ever-exposed to Benlysta at any point during the follow-up period, once exposed to Benlysta they will always be considered at risk. Any events accrued and all follow-up time after first Benlysta treatment has started will be allocated to Benlysta exposure. Follow-up time before first Benlysta exposure will be allocated to the comparison cohort. Therefore, a subject's exposure group will only change once if a subject moves from a comparison treatment ('Not exposed' onto Benlysta).

A limitation of this strategy is bias from mismatch of events to exposure arm since events occurring after switching off Benlysta are attributed to Benlysta exposure when subjects are no longer exposed.

**Programming Hints for derivation of essential variables needed for computation of incidence and events rates (presented in Section 7.1.5.1) under the ‘Ever-Exposed’ approach:**

- Subjects on Benlysta at enrollment will only have one exposure period (period=1) and Period Start Date = Enrollment Date (as ITT strategy).
- Subjects not on Benlysta at enrollment who do not switch on to Benlysta will only have one exposure period (period=1) and Period Start Date = Enrollment Date (as ITT strategy).
- Subjects not on Benlysta at enrollment who do switch on to Benlysta will have two exposure periods:
  - For period = 1, Period Start Date = Enrollment date, Exposure = Non-Benlysta and Period End Date = Benlysta start date -1
  - For period = 2, Period Start Date = Benlysta start date, Exposure = Benlysta and Period End Date = Last contact date\*.
- Identify or map events experienced during the study to a specific exposure period by checking the event onset within the period start and end interval.

Follow-up Period Start Date ≤ Event Date ≤ Follow-up Period End Date

NOTE: for incidence rate calculation, first event is retained for each exposure group (i.e. Benlysta and Non-Benlysta). This is only applicable for subjects with two exposure periods, i.e. subjects not on Benlysta at enrollment who do switch on to Benlysta.

- Calculate individual’s subject-years of follow-up for time spent in each exposure group as follows:
  - a) Subjects on Benlysta at enrollment:
 
$$\text{Exposed subject-years} = (\text{Last contact date}^* - \text{Enrollment Date} + 1) / 365.25.$$
  - b) Subjects not on Benlysta at enrollment who do not switch on to Benlysta:
 

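### No malignancy or NMSC analysis applies a lag or uses time since first-ever BENLYSTA dose, so early cancers are charged to BENLYSTA and a delayed effect would be diluted

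*SAP*

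**What the plan says.** **Attribution rule.** Protocol 8.3.2 sets the rule for NMSC and other malignancies: "all events will be attributed to BENLYSTA if the patient was ever exposed to BENLYSTA treatment prior to the event". SAP 9.2.1.3 implements it: "Any events accrued and all follow-up time after first Benlysta treatment has started will be allocated to Benlysta exposure". A comparison patient who switches is exposed from the BENLYSTA start date, and an event on that date counts. For patients already on the drug, "Subjects on Benlysta at enrollment will only have one exposure period (period=1) and Period Start Date = Enrollment Date (as ITT strategy".

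**Other strategies.** SAP 5.1 states "Primary analysis will be done on ‘Initial Exposure’ strategy for all endpoints", so Ever-Exposed is exploratory; it is also used for mortality. Malignancy and NMSC are further analysed by ITT, While On Initial Exposure and 14-week As-Exposed. Under SAP 9.2.1.1 and 9.2.1.2 none of these has a lag, and 14-week As-Exposed moves a cancer found more than 98 days after stopping to NON-BENLYSTA. The weighted analyses in SAP 7.3 use only ITT and While On Initial Exposure.

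**Room for more.** Protocol 8.3.2 adds: "Other risk windows (including risk windows for comparison treatment) may also be assessed and defined in the statistical analysis plan". The SAP defines no lagged window.

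**Tables and data.** Tables 24.410 to 24.412 give Ever-Exposed rates by time period, overall and separately for current users and initiators. Under SAP 7.1.5.1 follow-up for each period starts at enrollment, so the columns are cumulative. Protocol 6.1 collects the date needed for another time scale: "If the patient is receiving BENLYSTA, the date of first dose, and route of administration (IV or SC) will be recorded". SAP 5.6.2 already uses the earliest baseline BENLYSTA start date to separate current users from initiators.

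**The concern.** Protocol 1.3 gives malignancy as a particular reason for prolonged follow-up. For a cancer endpoint, a rule with no lag has two effects. A tumour already present at the first dose but found shortly afterwards is counted as a BENLYSTA case, which raises the BENLYSTA rate. Early person-time, in which a delayed effect could not yet appear, carries full weight, which pulls the rate toward the comparison rate. The two act in opposite directions, and the planned tables cannot separate them. A null result could then be read as reassurance about latencies that were never examined separately.

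The protocol itself shows that latency can matter in this disease. Section 1.1 describes a possible excess of hematological malignancy after immunosuppressive drugs, "particularly when the medication exposures were lagged by a period of 5 years (adjusted HR 2.29, 95% CI 1.02-5.15").

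**Working it through.** **Inputs.** 2,000 BENLYSTA and 1,000 comparison patients, 5 years of follow-up, 10% annual drop-out, no crossover, and 0.226 malignancies (excluding NMSC) per 100 patient-years, all from Protocol 8.2. The documents do not give a rate ratio, a lag of 1 or 2 years, or the share of current users. The values below are assumptions: ratio 2.0 after the lag and 1.0 before it, and all BENLYSTA patients initiators unless stated.

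**The plan's figures.** Person-years per patient = (1 - 0.9^5) / (-ln 0.9) = 0.40951 / 0.10536 = 3.887. Times 2,000 and 1,000 this is 7,773 and 3,887, against the stated 7,773 and 3,886. Expected malignancies: 0.00226 x 7,773 = 17.6 and 0.00226 x 3,886 = 8.8. The half-width 1.96 x sqrt(0.00226 x (1/7,773 + 1/3,886)) is 0.183 per 100 patient-years. With whole events (18 and 9) it is 0.185, which rounds to the stated 0.19.

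**Early person-time in initiators.** Year 1: (1 - 0.9) / 0.40951 = 24%. Years 1-2: (1 - 0.81) / 0.40951 = 46%.

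**Dilution.** Share beyond lag L: s = (0.9^L - 0.9^5) / 0.40951. Unlagged ratio = 1 + s x (2.0 - 1). If half of the BENLYSTA cohort are current users already past the lag, s is replaced by 0.5 + 0.5s.

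| Lag | s | BENLYSTA person-years beyond lag | Unlagged ratio, all initiators | Unlagged ratio, half current users |
|---|---|---|---|---|
| 1 year | 0.756 | 5,875 | 1.76 | 1.88 |
| 2 years | 0.536 | 4,167 | 1.54 | 1.77 |

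As a rate, with the 2-year lag and all initiators, BENLYSTA would show 0.226 x 1.54 = 0.35 per 100 patient-years instead of 0.226 x 2.0 = 0.45. With a 5-year lag s = 0: initiators contribute no person-time in this model.

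**Switchers.** For a patient who starts BENLYSTA 2 years after enrollment, the share of exposed time beyond a 1-year lag is (0.729 - 0.59049) / (0.81 - 0.59049) = 0.63. Beyond a 2-year lag it is (0.6561 - 0.59049) / 0.21951 = 0.30. Late switchers are diluted more than baseline initiators.

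**What the by-period tables would show.** With a 2-year lag in initiators, the cumulative ratio at 12, 24, 36, 48 and 60 months would be 1.00, 1.00, 1.30, 1.45 and 1.54. The rise is visible, but the post-lag value of 2.0 is not.

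**What a lagged analysis gains.** Wald intervals on the log rate ratio; detection means that the 95% interval excludes 1.

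- 2-year lag, unlagged analysis: 1.54 (0.72 to 3.29), detection 20%.
- First 2 years excluded in both cohorts: 2.0 (0.73 to 5.49), detection 27%.
- First 2 years excluded in BENLYSTA only: 2.0 (0.90 to 4.45), detection 40%. This treats the cohorts unequally, so the 27% figure is the fair one.
- Immediate effect, no latency: 2.0 (0.95 to 4.19), detection 45%.

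**The case against.** **The SAP follows the protocol.** Once exposed, always at risk is the protocol's rule, and other windows are optional. This stands: no required analysis is missing. Ever-Exposed is also exploratory. That limits the weight of the point but does not fill the gap, because the primary strategies have no lag either.

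**The issue is partly covered.** Current users (at least 62 days on treatment) and initiators (under 62 days) have separate Ever-Exposed tables. For BENLYSTA initiators, time from enrollment is within about two months of time from first dose, and differencing the cumulative columns of Table 24.412 gives approximate interval rates. This stands as a partial proxy. It makes no use of current users' prior duration and does not place late switchers by time since first dose.

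**Events are too few.** Even an immediate ratio of 2.0 has an interval that includes 1, and the SAP plans group rates with confidence intervals and no formal tests. This is correct: event count limits the malignancy analysis as much as the missing lag does. It argues for sensitivity status. The dilution applies to the BENLYSTA rate itself, whether or not a ratio is printed.

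**The hazard ratio of 2.29.** A reader might infer that the protocol's background reports a delayed BENLYSTA signal that the plan would hide. It does not. The result concerns hematological malignancy after immunosuppressive drugs; in the same cohort the hazard ratio for malignancy overall was 0.82 (0.50 to 1.36). Comparison patients receive immunosuppressants by eligibility, and Protocol Table 1-1 shows no hematological malignancy in any arm. The result is a reason to check latency. It cannot be used as a BENLYSTA rate ratio.

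**Conclusion.** The point holds as a cheap improvement. No malignancy or NMSC analysis sets a lag or runs on time since first-ever dose. In initiators 24% of person-time falls in year 1 and 46% in years 1-2; these shares rest only on the plan's drop-out assumption. The diluted ratios of 1.76 and 1.54 rest further on an assumed ratio of 2.0, assumed lags, an all-initiator cohort and no crossover. With half the cohort current users past the lag they become 1.88 and 1.77.

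Two stronger readings are not supported. First, not every BENLYSTA patient is counted from the first day of exposure: that is literal for switchers and approximate for initiators, while current users are counted from enrollment, at least 62 days after starting. Second, a latency of 5 years or more is not missed because of the attribution rule. It is missed in initiators because follow-up lasts 5 years; only current users with long prior use can inform it. The net direction of bias is also unknown, since early cancers and dilution work against each other.

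**What to change.** Add to SAP 9.2.1.3, as sensitivity analyses for malignancies excluding NMSC and for NMSC, with the unlagged tables kept:

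1. Ever-Exposed rates with 1-year and 2-year lags from first-ever BENLYSTA dose. Show lag-period events and person-time separately. In the comparison cohort, exclude the same early period after the start of qualifying treatment.
2. BENLYSTA rates by interval since first-ever dose (under 1, 1 to under 2, 2 to under 5, and 5 or more years). Current users enter at their actual time since first dose and are shown separately. Label this table descriptive, because its strata have no direct comparator.

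Report the BENLYSTA person-time at 5 or more years since first dose. Limit the malignancy conclusion to the latencies covered, and state that latency of 5 years or more cannot be assessed in initiators.

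**Cost.** SAP text and a few extra tables from dates already collected. Events per stratum will be few: at the reference rate, with all 2,000 BENLYSTA patients as initiators, the four intervals would hold about 4.3, 3.9, 9.4 and 0 malignancies (0.00226 x 1,898, 1,708, 4,167 and 0 person-years). Intervals will be wide, and the lagged results should be read as a check on the unlagged ones.
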